The most common structural pathologies that contribute to nasal obstruction are septal deviation (54%) and internal nasal valve collapse (14%), both of which increase resistance through the internal nasal valve. The internal nasal valve is defined by the junction of the nasal septum, caudal border of the upper lateral cartilage, and head of the inferior turbinate; it contributes to two-thirds of the total nasal resistance. [3] As per Poiseuille's law, resistance increases as a factor of the radius to the fourth power. As such, small changes to the dimensions of the internal nasal valve cause an exponential change in flow. In septal-deviation, the septum- the bony and cartilaginous structure that divides the nasal cavity- is deflected, dislocated off the maxillary crest, or off-center, causing a reduction in cross-sectional area of the internal nasal valve. Valvular collapse occurs when the lateral nasal wall paradoxically moves medially on inspiration at the level of the internal valve, causing a corresponding decrease in cross-sectional area and increase in nasal resistance. The cause of which can be congenital – from weak upper lateral cartilage or lack of dilator function, develop as a result of trauma, or occur post-operatively in patients following nasal surgery [8].

There are a number of over-the-counter consumer products that attempt to relieve this mechanical nasal obstruction in an effort to avoid surgery. One of the most popular external dilators is Breathe Right, a flexible strip that is adhered to the nose and stents the lateral walls of the nose outward to prevent internal nasal valve collapse [8]. Other existing solutions take the form of nasal cones and clips that act intra-nasally to stent the collapsed nasal valve. While studies show that these products are mostly effective in increasing nasal airflow, they are typically described as uncomfortable and carry social stigma due to visibility during use, leaving their use for an extended period of time limited [11].

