Participants are free to wear the assigned nasal dilator at their leisure beyond one hour, but must log the hours and activities performed while wearing the device (for example, “10am-11am exercising”). Patients are not required to wear a device in public at work or during exercise unless they feel comfortable doing so. All devices should be worn overnight. When the schnozzle is utilized at night, a modified version will be used where each portion inserted into the nares will be connected by an external bridge. This is to prevent posterior displacement of the device during sleep. Each morning, the participant will complete a survey summarizing their experience using the assigned device (Appendix B). If there is any discomfort, irritation, skin breakdown, or epistaxis the participant should stop wearing the device and contact the research team immediately.

Over the course of the first six days since the initial clinic visit, the participant will trial and log their use of each of the six nasal dilators. After at least six days (one day per device) participants will return to the office for an exit interview with the study team in regards to their subjective experience with each device. At the end of each trial day they will be asked to fill out a concluding survey (see appendix C). At their exit interview they will be asked to submit both appendix B and C for each device they trialed.

Before returning to the clinic for the conclusion of the study, participants may have several days without an assigned device. Participants are free to stop wearing all devices or use any device as they please as long as it is consistent with proper care and use of the device(s).

*b. Study duration and number of study visits required of research participants.*

This study requires two office visits – one to begin the study with baseline PNIF measurements, device fitting, PNIF with each device in place, and a perception survey. This will be followed up with a wrap up visit end the study with a concluding survey. Each patient will participate in the study for at least six days to trial each device, and the entire duration depends on an individual patients’ ability to return to the clinic, no more than two weeks.

Participants will be free to stop participating at any point during the study. Participants will have the option to be included in a list of individuals who would be interested and willing in participating in additional study sessions.

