*c. Blinding, including justification for blinding or not blinding the trial, if applicable.*

Patients will be blinded to the names of the devices tested to limit bias when they complete the surveys. They will also be blinded as to which device was designed by members of the research team.

*d. Justification of why participants will not receive routine care or will have current therapy stopped.*

The standard of care is to do nothing, use existing nasal dilator devices, or surgery. This one session comparison study of nasal dilators does not prevent patients from proceeding with the standard of care after the study session, and will familiarize them more thoroughly with available treatment options.

*e. Justification for inclusion of a placebo or non-treatment group.*

Participants will serially wear the prototype Schnozzle device and marketed nasal dilators, all of which are treatments. We will get a baseline NOSE and PNIF score from participants without any assistive devices in place, which serves as the placebo/ non-treatment arm of the study. Following the study session participants can continue to use currently marketed nasal dilators or proceed with planning surgery.

*f. Definition of treatment failure or participant removal criteria.*

Participants will be removed from the study if they experience substantial discomfort with the study devices, or if they experience any adverse events, such as epistaxis, or skin breakdown or if they would like to discontinue testing for any reason.

*g. Description of what happens to participants receiving therapy when study ends or if a participant's participation in the study ends prematurely.*

At the end of the study session participants will be able to continue using any of the marketed nasal dilator products currently on the market, and this study will not influence their ability to proceed with scheduling surgery if indicated and desired. They will not be able to continue using the Schnozzle nasal dilators at this time as it is still in early stage development and not widely produced or available.

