## **6. Drugs/ Substances/ Devices**

*a. The rationale for choosing the drug and dose or for choosing the device to be used.*

The control devices (Breathe Right strips, Sleep Right dilator, Mute dilator, Nozovent dilator, and Max Air nose cones) were selected from several other nasal obstruction products available on the market based on discussions with patients and opinion leaders in nasal airway obstruction due to their popularity and reported effectiveness. These are all legally marketed in the United States as Class I 510(k) exempt medical devices available over-the-counter.

The Schnozzle was developed as a non-invasive, discreet alternative to the current products available for nasal airway obstruction. Schnozzle is still in prototype form, and this testing will influence final design updates to improve the dilator before full-scale manufacturing and marketing. For this testing, Schnozzle prototypes will be produced using an FDA approved silicone.

Schnozzle is a Class I device not requiring FDA approval prior to use in humans. It fits into the existing internal nasal dilator classification as defined by Code of Federal Regulations (CFR) Title 21, Part 874 - Ear, Nose, Throat Devices, Subpart D - prosthetic devices, section 874.3900. According to this definition, a nasal dilator “provides relief from temporary causes of breathing difficulties resulting from structural abnormalities” through a mechanism that “decreases airway resistance and increases nasal airflow”. More specifically, the Schnozzle device fits into the internal nasal dilator subcategory. As stated in the FDA’s ruling, “the internal nasal dilator is constructed from metal or plastic and is placed inside the nostrils; it acts by pushing the nostrils open or by gently pressing on the columella”. The Schnozzle nasal dilator fits this definition, being a prosthetic device placed inside the nostril with the purpose of increasing nasal airflow.

As confirmed by Greenleaf Health, a regulatory consulting firm, Schnozzle can be considered Class I device exempt from 510(K) premarket notification.

- b. Justification and safety information if FDA approved drugs will be administered for non-FDA approved indications or if doses or routes of administration or participant populations are changed.* N/A
- c. Justification and safety information if non-FDA approved drugs without an IND will be administered.* N/A

Date: 7/6/20

Principal Investigator: [name]

Application Number: IRB00135539

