## 7. Study Statistics

### a. Primary outcome variable.

Peak Nasal Inspiratory Flow (PNIF) and Nasal Obstruction Symptom Examination (NOSE) score for each individual before the trial and while using each tested nasal dilator.

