### b. Secondary outcome variables.

Comfort, appearance, ease of use, and general favorability of each device.

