### c. Statistical plan including sample size justification and interim data analysis.

The purpose of this pilot study is to understand patient needs and preferences regarding nasal dilators, and to use this data to refine the design before potentially marketing the product. In this pilot study we plan to test 70 individuals with nasal valve collapse. Previous studies have demonstrated an ability to detect a statistically significant difference in PNIF with a power of 80% and an alpha of 0.05 with a sample size of 30 patients with nasal valve collapse. We aim to recruit 70 individuals, 35 patients with nasal valve collapse, 35 patients without nasal valve collapse with expected attrition of 5 patients in each cohort.[12] If we proceed to pursue statistical evaluation of the data we will use ANOVA with a  $p < 0.05$  predetermined as significant.

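### Section 4f takes a participant out of all six device trials for a problem that one device may have caused, and 7c does not say how the incomplete device sets are analysed

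*Combined protocol and SAP*

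**What the plan says.** - **Removal rule (4f).** "Participants will be removed from the study if they experience substantial discomfort with the study devices, or if they experience any adverse events". Epistaxis and skin breakdown are given as examples. The discomfort limb refers to devices in the plural. In the adverse-event limb any single event is enough.
- **Home instruction (4a, Study design).** For any discomfort, irritation, skin breakdown or epistaxis, the participant takes off the device in use and calls the team. The text does not say what happens to the remaining devices.
- **Schedule (4a, 4b).** PNIF is measured with all six devices at the first visit. The six devices are then used at home, one per day in random order, over the first six days, with a survey for each. Total duration depends on the participant's "ability to return to the clinic, no more than two weeks".
- **Outcomes (7a, 7b).** The primary outcomes are PNIF and NOSE "for each individual before the trial and while using each tested nasal dilator". The secondary outcomes are "Comfort, appearance, ease of use, and general favorability of each device".
- **Analysis (7c).** "If we proceed to pursue statistical evaluation of the data we will use ANOVA", at a 5% level. The sample size allows for "35 patients without nasal valve collapse with expected attrition of 5 patients in each cohort". There is no repeated-measures form, analysis set or rule for incomplete device sets.
- **Halting (7d).** The study stops if a large share of patients cannot complete it because of device comfort or adverse outcomes. No threshold is given.

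**The concern.** In a six-device within-person comparison, removing the person because of one device also removes that person's view of the devices not yet tried. Some events covered by 4f say little about those devices. Breathe Right is described in section 3 this way: "One of the most popular external dilators is Breathe Right, a flexible strip that is adhered to the nose". Schnozzle is described in 6a as "being a prosthetic device placed inside the nostril with the purpose of increasing nasal airflow". Skin breakdown under the strip would, under 4f, end testing of a device that does not touch that skin.

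The loss is also not random. Removal depends on how badly a device was tolerated, and comfort is one of the outcomes compared. If the ANOVA is run on complete sets only, the people who found a device worst leave that device's mean, which flatters the device causing most removals. The stated purpose of this pilot is to learn patients' needs and preferences and refine the design, so these ratings matter.

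**Working it through.** **1. What the sections require together.** 4a and 4f overlap on skin breakdown and epistaxis: one acts on the device, the other on the participant. They can be reconciled (take off the device, call the team, and the team then applies 4f), but that ends in removal. Section 8a lets participants refuse any device. That is voluntary and does not override 4f.

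**2. Which outcomes are exposed.** A removal at home leaves first-visit PNIF complete. It loses the home ratings of later devices. It probably also loses NOSE for those devices, because 4a describes only PNIF being repeated with each device in clinic. That is an inference, since the appendices are not shown. A removal during the first-visit fittings would lose PNIF for later devices too.

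**3. The plan's own figure.** 30 evaluable + 5 attrition = 35 per cohort, and 35 × 2 = 70. This reproduces. The 30 is justified only by detection of a PNIF difference.

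**4. Device trials lost per removal.** With random order the triggering device is equally likely to be in any of six positions.
- Triggering device still rated: (5+4+3+2+1+0)/6 = 2.5 trials lost.
- Triggering device not rated: 2.5 + 1 = 3.5 trials lost.

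Take five removals in a cohort of 35, purely as an illustration. The loss is 12.5 of 35 × 6 = 210 trials (6.0%), or 17.5 of 210 (8.3%).

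**5. Loss to each other device.** If one device removes a share q of its users, it precedes any given other device half the time, so that device loses about q/2 of its ratings. At an assumed q of 10% this is 5% (1.75 of 35). At 20% it is 10% (3.5 of 35).

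**6. Worst-case bias.** Assume normal ratings with SD 1, five of 35 removed by one device (q = 5/35), these being exactly its five lowest raters, and complete sets only. Then z = −1.068 and the normal density there is 0.2256.
- Triggering rating not kept: 0.2256/(1 − 5/35) = 0.263 SD too high.
- Triggering rating kept: one removal in six falls on the last device and leaves a complete set, so (5/6 × 0.2256)/(1 − 5/6 × 5/35) = 0.188/0.881 = 0.213 SD too high.

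A comparator correlated ρ with that device shifts by ρ times as much, so the error in the difference is (1 − ρ) times these values. At ρ = 0.5 it is 0.13 SD (not kept) or 0.11 SD (kept). At ρ = 0 it is the full 0.26 or 0.21 SD. For scale, the standard error of a paired difference with 30 complete sets is √(2(1 − ρ)/30), which is 0.18 SD at ρ = 0.5 and 0.26 SD at ρ = 0.

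**7. A milder case.** A simulation assumed correlation 0.5, 2% removal on five devices, 10.7% on the sixth, and triggering ratings kept. The poorly tolerated device kept 95.8% of its ratings and the others about 92%. A true difference of −0.80 SD became −0.74 on complete sets (0.06 too small) and −0.83 on simple means of available ratings (0.03 too large).

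**The case against.** The strongest reply is that 4f is a safety rule in a pilot of a prototype and that the plan already contains device-level provisions. Participants are told to take off the device, may refuse any of them, and hand in forms for each device they tried, which allows for partial sets. A sore nose could also contaminate the next device's comfort rating. Section 8a expects discomfort to be uncommon and mild and epistaxis to be unlikely. The missing-data gap in 7c would exist whatever 4f said.

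Much of this stands. Full withdrawal after epistaxis or intranasal injury is a sensible precaution, and low event rates would make the effect small. The plural in the discomfort limb also leaves room to read it as trouble with the devices in general. But none of the device-level provisions says that a participant continues after a 4f event, and the adverse-event limb is mandatory. Contamination by soreness is a reason for a pause judged by a clinician, and does not require removal for every event.

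Two stronger readings are tempting, and the documents support neither. A reader might infer that removals at home use up the allowance of 5 in 35 and leave the trial underpowered. That allowance was set for PNIF, which is finished before home use begins, and no sample size was justified for the home ratings. A reader might also infer that the device comparisons will be biased. That requires removals to concentrate on one device and only complete sets to be analysed, and the plan specifies neither. If removals are spread evenly over the devices, the differences are not biased.

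**Conclusion.** The point holds as a minor one. Followed as written, 4f loses later devices' home ratings for a reason tied to a compared outcome, 4a and 4f give unaligned instructions for the same events, and 7c has no rule for the result. The loss is 2.5 or 3.5 device trials per removal, depending on whether the triggering device is rated. The 0.21 to 0.26 SD shift is a ceiling. It rests on five removals, all from one device and all its lowest raters, on normal ratings, and on complete-set analysis. The number of removals is an assumption, because the documents give no event rate. PNIF is not at risk except from removals during the first-visit fittings.

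**What to change.** - **4f.** Substantial discomfort with one device, or skin breakdown confined to the outside of the nose under the adhesive strip, ends use of that device only. The participant goes on to the next scheduled device once the study clinician judges the problem settled. Epistaxis or breakdown inside the nose ends use of all internal devices or, if the sponsor prefers, all testing. Anyone stopping early is asked for Appendix B and C for every device tried, including the one stopped. Participants may still leave at any time.
- **4a.** Align the home instruction with 4f, and let the six device days extend within the two-week limit in place of the first six days.
- **7c.** Compare devices with a mixed model, participant as random effect, on all available ratings, and report stops by device. Collecting the stopped device's rating matters here: the loss then depends on data that were observed, which such a model can accommodate.
- **7d.** Count device stops for discomfort or adverse events toward the halting rule, so that fewer removals do not weaken it.

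**Cost.** A few sentences, with no new visit or form. Six device days within two weeks leave up to 14 − 6 = 8 days for a pause, so a few participants would finish some days later. Possible carry-over of soreness is left to clinical judgement. The gain is limited to discomfort and external-skin events, because bleeding and intranasal injury would still end most or all testing.

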### d. Early stopping rules.

After 5 and 10 participants complete testing we will evaluate the data to look for themes and determine if further testing is likely to yield additional information. If a large percentage of patients are unable to complete the study due to complaints with device comfort or due to previously defined adverse outcomes we will halt the study.

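### Removal for discomfort or an adverse event, with device surveys handed in only at the exit interview, is likely to lose the worst comfort ratings and modestly understate the least tolerated device's deficit

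*Combined protocol and SAP*

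**What the plan says.** Section 4f ends participation in the whole study, not just use of one device: "Participants will be removed from the study if they experience substantial discomfort with the study devices, or if they experience any adverse events".

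Section 4a covers the home phase. One device is assigned per day in randomized order. Appendix B is filled in each morning and Appendix C at the end of each trial day. The only stated hand-in point is the last visit: "At their exit interview they will be asked to submit both appendix B and C for each device they trialed". On its timing: "After at least six days (one day per device) participants will return to the office for an exit interview with the study team". When something goes wrong, 4a says: "If there is any discomfort, irritation, skin breakdown, or epistaxis the participant should stop wearing the device and contact the research team immediately". It asks for no rating or form at that contact.

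Section 4g, whose heading includes premature end of participation, deals only with later access to devices and surgery. Section 7b lists the secondary outcomes: "Comfort, appearance, ease of use, and general favorability of each device". Section 7c makes the analysis conditional ("If we proceed to pursue statistical evaluation of the data we will use ANOVA") and gives no rule for people with partial data. Comfort-related non-completion appears once in Section 7, as a trigger in 7d for halting the study: "If a large percentage of patients are unable to complete the study due to complaints with device comfort". It is not counted by device.

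**The concern.** A participant who finds a device very uncomfortable is, for that reason, taken out before the visit at which the forms are collected. Whether a rating reaches the database then depends on the rating itself. Three kinds of rating are affected: the one for the device that caused the problem, those for devices already tried (written down but perhaps never handed in), and those for devices not yet tried, which never exist.

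The device that triggers most removals loses most of its low ratings. Its mean rises more than the others' means, so its comfort deficit shrinks. Section 7c says the purpose of the pilot is "to use this data to refine the design before potentially marketing the product", and for that purpose the reports of people who could not wear a device are among the most informative the study will produce.

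**Working it through.** **The plan's own figure.** Section 7c: 30 + 5 expected losses = 35 per cohort, and 2 × 35 = 70. Expected attrition is therefore 5/35 = 14.3%, or 10 of 70. No causes are given for it. The plan states no figure for comfort, so everything below rests on assumed scores.

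**Assumed inputs (not in the documents).** Comfort on 0-10, higher is better. Five devices have mean 7 and one has mean 7 − d. The residual SD is 1.77 and the participant SD 1.25, so the SD of a within-person device difference is √2 × 1.77 = 2.5. Removal follows the first rating of 2 or less. All forms of a removed person are lost. From the plan: 70 people, six devices, random order.

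**Check by hand, d = 2.** The SD of a single rating is √(1.77² + 1.25²) = 2.17.
- Chance of a rating of 2 or less on the worse device: Φ((2 − 5)/2.17) = Φ(−1.38) = 8.3%, or 5.8 of 70.
- The same for each other device: Φ((2 − 7)/2.17) = Φ(−2.31) = 1.05%, or 0.7 of 70.
- Cutting off that tail alone raises the worse device's mean by 2.17 × φ(1.38)/Φ(1.38) = 2.17 × 0.153/0.917 = 0.36, and each other device's mean by 2.17 × 0.028/0.989 = 0.06.

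The gap closes by less than 0.36 − 0.06 = 0.30, because a removed person's other ratings go too, and they also tend to be low.

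**Simulation of the full rule (central case).**

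| True deficit | Removed of 70 | Own mean overstated by | Deficit shown, all forms lost | Half of removed return forms |
|---|---|---|---|---|
| 2 | 8.1 (5.3 because of that device) | 0.40 | 1.81 | 1.91 |
| 1 | 5.0 | 0.22 | 0.94 | 0.97 |
| 0 | 3.7 | 0.13 | 0.00 | 0.00 |

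At d = 2 the deficit is short by 2 − 1.81 = 0.19, or 9.5%. The other devices' means are overstated by 0.40 − 0.19 = 0.21.

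**Range.** With a difference SD of 2 to 3 and removal at 1 or less or at 2 or less, the 2-point deficit shows as 1.72-1.97 and the 1-point deficit as 0.89-0.99, with 0.3 to 14.0 people removed. The sign reversed in at most 0.1% of runs.

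A separate simulation (400,000 participants, rating SD 2, within-person correlation 0.2 or 0.5) gave 1.81-1.95 for a true 2.0 with cut-offs 1 and 2. A cut-off of 3 gave 1.64-1.77, but removed 20-23% of people, more than the 14.3% total attrition the plan expects.

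**What collection at the stop recovers.** If earlier forms come back but the offending device's form is missing, the bias stays: in that second simulation a true 2.0 shows as 1.79-1.82 at cut-off 2. If the offending device's rating is kept, simple means of available ratings give 2.01-2.09 and a within-participant analysis gives 1.92-1.99. The rating taken at the stop is what matters.

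**The case against.** The strongest reply is that the effect is small for a pilot. The standard error of one device comparison is about 2.5/√70 = 0.30, so the central bias is 0.19/0.30 = 0.6 of a standard error at d = 2 and 0.06/0.30 = 0.2 at d = 1. A 2-point deficit would still be seen. That stands, and it limits the weight of the point.

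The loss of forms is also an assumption. A reader might infer that removed participants' ratings are certain to be lost or are discarded by rule. The documents do not say so: the forms are filled in daily, the team must be contacted at once, and staff could ask for them. Appendices B and C are not in the reviewed text and might carry return instructions. Likely is as far as the text goes.

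Other records soften the problem. Adverse events go to the principal investigator (8c), wear is logged (4a), each device is worn for five minutes in clinic before home use (4a), and data are reviewed after 5 and 10 participants (7d). None of these yields a comfort rating by device after a removal. Section 8a expects discomfort to be uncommon and minor; if so, little is lost. Removals for adverse events that do not track comfort would shrink the bias further.

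A reader might also infer that 4f should be loosened so that discomfort stops only the device. The bias does not require that. 4f protects participants wearing a prototype, and collecting the forms is enough.

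**Conclusion.** The point holds as a modest gap in how a secondary outcome is collected. The removal rule and the single hand-in point together make loss of the worst comfort ratings likely, and the direction of the resulting bias is towards understating the least tolerated device's deficit. Under the assumed scores and complete loss of removed people's forms, a 2-point deficit shows as about 1.7-2.0 and a 1-point deficit as about 0.9-1.0. The size depends on the assumed scale, SD, removal threshold and share of forms lost. It is roughly halved if half the forms return, and between-device bias vanishes if removals fall evenly over devices.

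Three stronger readings are not supported. The ranking of devices is not put at risk, because the sign is kept. Nothing in the documents shows that Schnozzle would be the device flattered, since they do not say which device is least tolerated. And the in-clinic PNIF comparison is largely untouched, because all six devices are measured at the first visit, before the home trial.

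**What to change.** In 4a/4f, add that anyone who stops a device or is removed completes Appendices B and C for that device at the time of contact, marked as an early-stop rating, and returns all forms already completed.

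In 7c, add that the comfort summary includes all available ratings from everyone who started each device, and that the report gives, for each device, the number of stops or removals for discomfort and for adverse events over the number who wore it.

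Leave the 4f removal criterion as it is.

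Cost: a few sentences, one small table by device, and slightly more data collection at early exit. The downside is that some ratings will reflect only partial wear, which is why they should be flagged.
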